	
Variables to determine the primary endpoint:
 
For the time to medical treatment failure endpoint:
 
 • Start date of larotrectinib treatment for the SCOUT study and start date of chemotherapy (first line) for the external historical control cohort(s), and whichever comes first: 
 ○ Start date of a post-treatment³ systemic anti-cancer therapy, if any, or, ○ Start date of a post-treatment³ radiation therapy, if any, or, ○ Date of a post-treatment³ mutilating surgery, if any, or, ○ Date of death due to any cause, if applicable. 
Variables to determine the secondary endpoints:
 
For the time to subsequent systemic treatment endpoint:
 
 • Start date of larotrectinib treatment for the SCOUT study and start date of chemotherapy (first line) for the external historical control cohort(s), and, • Start date of a post-treatment³ systemic anti-cancer therapy, if any. 
For the time to mutilating surgery including limb amputation endpoint:
 
 • Start date of larotrectinib treatment for the SCOUT study and start date of chemotherapy (first line) for the external historical control cohort(s), and, • Date of a post-treatment³ mutilating surgery including limb amputation, if any. 
For the time to radiation therapy endpoint:
 
 • Start date of larotrectinib treatment for the SCOUT study and start date of chemotherapy (first line) for the external historical control cohort(s), and, • Start date of a post-treatment³ radiation therapy, if any. 
For the time to complete surgical resection (excluding amputation) endpoint:
 
 • Start date of larotrectinib treatment for the SCOUT study and start date of chemotherapy (first line) for the external historical control cohort(s), and, • Date of a post-treatment³ complete surgical resection (excluding amputation), if any.
--	--

³ After the start of larotrectinib treatment for the SCOUT study or after the start of chemotherapy (first line) for the external historical control cohort(s).

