9.7.6 Sensitivity analysis

As the choice of index date and statistical method may affect the results, the following sensitivity analysis will be conducted in order to explore the impact of methodological choices on the results. A consistency in the findings regarding the treatment effect between the main analysis and the sensitivity

analyses should instil confidence in the primary results. Inconsistencies in the results will be explored through further analysis. Further details will be described in the SAP.

- Choice of index date:

As the majority of larotrectinib patients will be receiving 2nd line therapy, this analysis attempts to maximize consistency between treatment groups in terms of line of therapy while committing to the inclusion of all available patients. For SCOUT patients, the index date will be defined as the start date of larotrectinib, regardless of line of therapy. In the external historical control cohort(s), the index date will represent start of chemotherapy. However, control patients who take a second line of therapy will have their index date set at the start of second line, in order to provide a close comparison with the larotrectinib group prior to any adjustment using IPTW. A caveat of this analysis is that it may fail to capture some clinically relevant events, for example control subjects receiving a second line of treatment.

- Subgroup analysis:

For the patients treated with a second line or more of systemic therapies, the index date will be defined as the second line of treatment in both the treatment and control groups.

This analysis will reflect the current reimbursement scope of larotrectinib, i.e. in patients who are refractory or in relapse.

- Statistical method:

A plot of the distribution of IPTW weights by group will be used to identify very large weights. Trimming at 5% level will be considered, which amounts to dropping the individuals with the most extreme PS values in both the treatment and control groups, as they may lack a match in the other group. Weight truncation will also be explored that reduces any 'large' weight down to a maximum weight. Therefore, in addition to the main analyses, the following sensitivity analyses will also be considered:

- a. IPTW (5% trimming)
- b. IPTW (truncating large weights)

A consistency in the findings regarding the treatment effect between the main analysis and the sensitivity analyses should instil confidence in the primary results.

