3.1.1 Phase 1 Dose Escalation and Dose Expansion

Phase 1 is a sequential-cohort dose escalation study designed to identify the maximum tolerated dose (MTD) through incidence and characterization of DLT. The adverse events (AE) defining dose limiting toxicity (DLT) are defined in integrated clinical study protocol (CSP) amendment, version 12.0, section 3.1.1.4.

Larotrectinib is administered twice daily (BID) in either an oral liquid or capsule form. Escalation in Phase 1 was to proceed through 5 planned dose levels or until the MTD was reached. When the optimal dose was thus identified, a Phase 1 expansion cohort of up to 18 patients was recruited to further

define the safety profile. Further details on the design of Phase 1 can be found in the integrated CSP amendment.

Individual patients will continue daily larotrectinib dosing until progressive disease (PD), unacceptable toxicity, or other reason for treatment discontinuation. All treated patients will undergo a safety follow-up visit at 28 days (\pm 7 days) after the last dose. Patients will be followed for long-term survival.

3.1.2 Phase 2

Phase 2 is an expansion study in 3 selected cohorts of pediatric patients with tumors bearing *NTRK* fusions: IFS, other extracranial solid tumors, and primary CNS tumors. At least 30 patients less than 18 years of age with a primary CNS tumor harboring an *NTRK* gene fusion, including 15 patients with high-grade gliomas (HGG) and another 15 patients with low-grade gliomas (LGG) were planned for enrollment to satisfy the PIP commitment that would show larotrectinib as a safe and effective treatment with significant anti-tumor activity and durable clinical benefit in children with a primary CNS tumor.

The Phase 2 study structure consists of screening, the treatment period, safety follow-up, and long-term follow-up until the study is closed. On-going safety (referred to as the “active safety follow-up” and described in integrated CSP amendment, version 12.0, section 7.6.1), survival, and subsequent anticancer therapies will be assessed during the long-term follow-up.

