Larotrectinib is administered as an oral capsule or a liquid formulation at the recommended dose determined in Phase 1 (100 mg/m²; not to exceed 100 mg BID). Cycles are 28 days of continuous BID dosing. Patients undergo periodic radiologic evaluation and ongoing safety assessments as outlined in the protocol. Individual patients will continue daily larotrectinib dosing until PD, unacceptable toxicity, or other reason for treatment discontinuation, as outlined in integrated CSP amendment, version 12.0, section 6.4.

Patients with locally advanced disease and a response of at least a partial response (PR) for a period of one year after PR is initially confirmed may have their larotrectinib treatment withheld, a “wait and see” period, after discussion with the Sponsor. Patients with LGG and a response of stable disease (SD) for a period of at least 2 years after SD is initially confirmed, may similarly have their larotrectinib treatment withheld. Patients in the “wait and see” period will continue to undergo periodic radiologic evaluation and ongoing safety assessments as outlined in section 7.8 of the protocol. If a patient in this “wait and see” period is noted to have evidence of radiographic disease progression, the patient may restart larotrectinib. At the time of larotrectinib re-initiation, the patient will restart all per protocol assessments as delineated for patients on active treatment. Patients who reinitiate larotrectinib treatment are permitted to have their larotrectinib treatment stopped again.

Patients who undergo surgical resection resulting in negative margins may have their study treatment stopped and continue to undergo periodic radiologic evaluation and ongoing safety assessments as outlined in section 7.7 of the protocol. These patients are permitted to restart study treatment, if they experience PD, after discussion with the Sponsor. At the time of larotrectinib re-initiation, the patient will start all assessments per protocol as delineated for patients on active treatment.

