6.2 Analysis of Primary Variable(s)

6.2.1 Primary Endpoint

The primary endpoint of the study is the time to medical treatment failure: defined as the time (months) from the start of treatment to the date of the earliest event from: subsequent systemic treatment, radiation therapy, mutilating surgery or death due to any cause.

The **index** date of the analysis of the primary endpoint will be defined as either the start date of larotrectinib treatment (for patients in the SCOUT study, regardless of line of therapy) or start date of chemotherapy (first line) for the external historical control cohorts. The end date is defined as the earliest of the following endpoints:

- Start date of a post-treatment systemic anti-cancer therapy, if any, or,
- Start date of a post-treatment radiation therapy, if any, or,
- Date of a post-treatment mutilating surgery, if any, or,
- Date of death due to any cause, if applicable.

Patients who do not record an event will be censored at the last known alive date.

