6.3.1 Time to Subsequent Systemic Treatment

The endpoint, time to subsequent systemic treatment, will be defined as the time from start date of larotrectinib (for SCOUT) or start date of chemotherapy (for historical control cohorts) till the start

date of a post-treatment systemic anti-cancer therapy, if any. Patients who do not take a subsequent systemic treatment will be censored at the last known alive date.

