6.7 Additional Analyses Planned to be Reported Outside the Study Report

Not applicable.

7. Document History and Changes in the Planned Statistical Analysis

The complementary analysis on patients with IFS or other STS with *NTRK* gene fusion will no longer take place as there is only one STS patient in the Curie Database and none in the CWS. In its place, analyses will be performed on the population of patients with IFS having documented *NTRK* gene fusion.

The protocol described a sensitivity analysis on choice of index date of the primary endpoint, for subjects in either arm who are treated with a second line or more of systemic therapy or larotrectinib. The index date was specified as the start of second line in both groups. However, as shown below in 2, fewer control subjects received a second line than anticipated, and a larger number of subjects in SCOUT took larotrectinib as the secondline therapy. Therefore, the analysis would have had an unbalanced sample size at N=32 versus 8. In addition, 14 of the 32 larotrectinib subjects start at line 3 to 6, leading to a conservative analysis that unduly favors the control group.

In order to provide a more balanced analysis, we propose to replace this sensitivity analysis for the choice of index date with the sensitivity analysis based on exact matching on the line of therapies, approach as detailed in Section 6.2.5. A subgroup analysis was planned in those treated with second line of treatment in both groups. A similar subgroup analysis will be conducted when comparing first line Larotrectinib patients versus external controls taking at least 1 line of therapy, which was added to Section 6.2.5.

Table2 Line of Therapy

	Larotrectinib	Control
1st Line	19 (37%)	34 (81%)
2nd Line or Higher	32 (63%)	8 (19%)

8. References

- [1] Rosner B. (2006). *Fundamentals of Biostatistics*. (6-th edition). Thomson Brooks/Cole.

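### Does the SAP need to say whether restarting larotrectinib counts as a subsequent systemic treatment in the primary endpoint?

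*SAP*

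**What the plan says.** SAP 6.2.1 defines time to medical treatment failure as the earliest of four events. The first is "Start date of a post-treatment systemic anti-cancer therapy, if any, or"; the others are radiation therapy, mutilating surgery and death. A patient with none of these is censored at the last known alive date. SAP 6.3.1 applies the same idea to a secondary endpoint: "Patients who do not take a subsequent systemic treatment will be censored at the last known alive date".

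A footnote to the variables in the protocol abstract explains post-treatment by timing alone: "After the start of larotrectinib treatment for the SCOUT study or after the start of chemotherapy (first line", in the control cohorts).

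SAP 3.1.2 (Phase 2) describes two routes back to larotrectinib. A patient in the treatment pause who "is noted to have evidence of radiographic disease progression, the patient may restart larotrectinib". For patients who stopped after resection with negative margins, "These patients are permitted to restart study treatment, if they experience PD, after discussion with the Sponsor". The same section says of long-term follow-up that "survival, and subsequent anticancer therapies will be assessed during the long-term follow-up".

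Neither document says expressly whether a restart, or renewed use of the same regimen in a control, is a subsequent systemic treatment.

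**The concern.** Two readings seem open. Taken alone, the footnote makes any systemic therapy begun after the index date eligible, so a restart could be an event. On the other reading a restart resumes the index treatment, and a SCOUT patient who progresses and is treated again stays event-free until the last known alive date.

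On the second reading the groups may appear to be treated differently, because a control who moves to second-line chemotherapy has an event. Protocol 9.7.6 treats that as clinically relevant: it warns that moving the control index date to second line means that "it may fail to capture some clinically relevant events, for example control subjects receiving a second line of treatment". SAP section 7 shows that such controls exist; it says of the second-line comparison that "the analysis would have had an unbalanced sample size at N=32 versus 8".

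So few larotrectinib events are expected that reclassifying one or two patients would visibly move the hazard ratio. SAP 6.2.5 varies weights, line matching and subgroups, but never the event definition. A rule left open might also be settled after outcomes are known.

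**Working it through.** **1. Reproduce the plan's own figures.** SAP section 4 gives n1 = 49, n2 = 42, pE = 0.04, pC = 0.19, IRR = 0.25 and alpha = 0.05, with Power = Φ(√(km)·|IRR − 1|/(k·IRR + 1) − 1.96).

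- k = 49/42 = 1.167. m = 49 × 0.04 + 42 × 0.19 = 1.96 + 7.98 = 9.94.
- √(1.167 × 9.94) = 3.405. 3.405 × 0.75/1.292 = 1.977. Φ(1.977 − 1.960) = 50.7%; the SAP states 51%.
- With unlimited controls, km tends to 49 × 0.19 = 9.31 and power to Φ(3.051 × 0.75 − 1.960) = 62.9%, as stated.

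The planning figures are sound and imply about 2 larotrectinib and 8 control events.

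**2. Size of the effect if restarts were counted.** Let r be the number of restarts counted as extra larotrectinib events and c the number of control events. Implied HR = ln(1 − (2 + r)/49)/ln(1 − c/42), with SE of log HR ≈ √(1/(2 + r) + 1/c). Values of r, and c = 12, are assumptions; the documents give no restart counts.

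| r | HR, c = 8 | approx. 95% limits | HR, c = 12 | approx. 95% limits | ratio to r = 0 |
|---|---|---|---|---|---|
| 0 | 0.20 | 0.04–0.93 | 0.12 | 0.03–0.55 | 1 |
| 1 | 0.30 | 0.08–1.13 | 0.19 | 0.05–0.67 | 1.52 |
| 2 | 0.40 | 0.12–1.34 | 0.25 | 0.08–0.79 | 2.04 |
| 3 | 0.51 | 0.17–1.56 | 0.32 | 0.11–0.91 | 2.58 |

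If restarts are not counted, the estimate stays in the first row. Counting same-regimen re-treatments in controls works the other way. At c = 8, four of them would offset one counted restart: ln(1 − 3/49)/ln(1 − 12/42) = 0.19. Table 2 in SAP section 7 totals 51 larotrectinib patients (19 + 32), not 49; using 51 gives 0.19, 0.29, 0.39 and 0.49 at c = 8.

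**3. Which reading the text supports.**

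- The footnote cannot be the whole test. If any systemic therapy given after the start of chemotherapy qualified, every later cycle of the first-line regimen would be a failure. It fixes timing, not what counts as another treatment.
- The governing words are next systemic treatment (Protocol 8.1, SAP section 2) and subsequent systemic treatment (Protocol 9.1.1, SAP 6.2.1). Both point to a treatment other than the index one.
- SAP 3.1.2 uses a different vocabulary for the pause: study treatment is withheld, restarted or re-initiated, and the patient returns to on-treatment assessments. Subsequent anticancer therapies are named separately, under long-term follow-up.

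**4. Whether the groups are treated alike.** The control counterpart of a restart is renewed use of the same regimen, not a move to second line. A SCOUT patient who moves to another agent has an event, as does a control who changes regimen. The 8 controls at second line or higher in Table 2 are not described by regimen, so they neither establish nor exclude same-regimen re-treatment.

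**5. How far restarts could matter.** The pause-and-restart text sits in the Phase 2 section only; the Phase 1 text in SAP 3.1.1 describes dosing until progression or another reason to stop. SAP 3.1 draws patients from both phases, so fewer than 49 may be eligible. Apart from a separate provision for low-grade glioma, which does not concern IFS, the pause route needs locally advanced disease and a response held for a year after confirmation.

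**6. What already covers it.** Both restart routes follow progression. SAP 6.3.6 (rule 5) counts progression as a PFS event in both groups, and SAP 6.3 analyses PFS with the primary endpoint's weights.

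**The case for a change.** The strongest opposing argument comes from the endpoint's own rationale. Protocol 7.8 calls further treatment upon progression a marker of failure, and a restart is exactly that. Leaving it uncounted keeps a patient who has progressed and been treated again event-free. Two programmers could derive different datasets, PFS is only exploratory, and the SAP's authors already knew how many controls had reached second line. A clarifying sentence would cost almost nothing.

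Part of this stands. The classification is not written down, and the endpoint then measures time to a different treatment rather than time to any renewed treatment. That is still a coherent endpoint and a defensible one. The argument does not show that the natural reading biases the comparison, because the same convention exempts a control's return to the same regimen. It also does not show that any restart occurred. A count of restarts by group and a sensitivity run would be informative, but they are additions. For restarted patients the run would largely repeat PFS at a slightly later date, and it would need control relapse and re-treatment dates that may be less complete (Protocol 9.9).

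**Conclusion.** The gap is real but does not call for a change. The wording already leans towards treating resumed larotrectinib as index treatment, and a competent analyst would apply the same convention to controls. The illustrated shift, a factor of 1.52 for one counted restart and 2.04 for two, arises only if the less natural reading is adopted and restarts occurred. It assumes unweighted data, constant hazards, equal follow-up, no restarted patient already failing on another component, and a planning rate of 0.04 that does not already include restarts. Restarts by the pause route would come late and no follow-up durations are given, so equal follow-up and constant hazards are doubtful. The planned analysis is weighted, with a bootstrap standard error.

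An upper limit that crosses 1 decides nothing here: SAP section 4 and Protocol 9.7.5 set no formal hypothesis, and the protocol abstract says that results are exploratory. The conclusion rests on one reading being used in both groups. SCOUT's own protocol and the Data Management Plan, to which the SAP defers, could not be checked and may already settle how restarts are coded.

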3.1 SCOUT study

The pediatric subgroup of patients from both phase I and II of the SCOUT study, having IFS, or with other STS for complementary analyses described in [sections 5.1.1](#) and [5.1.2](#), will form the larotrectinib population in the analysis.

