4.3.2 Time to Event Data

No imputation will be performed for missing tumor response evaluations or dates.

The last known alive date (LKAD) is defined as the latest date indicating that the patient is still alive, among all available visit dates and other dates pertaining to a patient record (e.g. AEs) in the database. Partial documented dates (i.e. with day only missing) will be imputed using the first day of the month.

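### The primary endpoint is censored at a date that shows only that the patient was alive, so any time in which treatment failure was not ascertained counts as failure-free

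*SAP*

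**What the plan says.** SAP 6.2.1 defines failure as the earliest of "subsequent systemic treatment, radiation therapy, mutilating surgery or death due to any cause". Event-free patients are handled in one sentence: "Patients who do not record an event will be censored at the last known alive date". SAP 4.3.2 defines the last known alive date as "the latest date indicating that the patient is still alive, among all available visit dates and other dates pertaining to a patient record", with adverse event entries as the example.

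The same date censors time to subsequent systemic treatment, mutilating surgery, radiotherapy and complete resection (SAP 6.3.1 to 6.3.4), and OS (SAP 6.3.5). PFS is treated differently: SAP 6.3.6 censors at the last tumor assessment, and at the last one before a new therapy if that starts first. The protocol gives censoring dates for OS (9.1.2) and PFS (9.1.3) but none for the primary endpoint (9.1.1, 9.3.1), so the SAP rule is the only one.

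On follow-up, SAP 3.1.1 says of SCOUT Phase 1, after the safety visit at 28 days: "Patients will be followed for long-term survival". For Phase 2, SAP 3.1.2 says that "survival, and subsequent anticancer therapies will be assessed during the long-term follow-up". SAP 3.1 puts both phases into the larotrectinib arm. Neither document says how the *Institut Curie* or CWS sources recorded later therapy, radiotherapy or surgery during follow-up.

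**The concern.** Three of the four failure types are not death. A record that a child is alive on some date says nothing about whether another systemic therapy, radiotherapy or mutilating surgery has taken place by then. The rule is right for OS. For the primary endpoint it is right only if failure status was known up to the same date.

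Where it was not, a patient stays in the risk set while non-fatal failures could not be seen. The denominator grows and the numerator does not, so that arm's failure rate is understated. If the two arms differ in how completely they were followed, the hazard ratio is biased. The arms are a monitored trial and two historical databases, so a difference is plausible. The sensitivity analyses in SAP 6.2.5 cover weights, line-of-therapy matching and line subgroups, and the bias analysis in SAP 6.5 covers unmeasured confounding. None of them varies the censoring rule, so the problem would not show in the report.

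**Working it through.** **1. The plan's own figure.** SAP section 4 gives N=49 SCOUT and N=42 control patients, failure probabilities 0.04 and 0.19, hazard ratio 0.25 and two-sided alpha 0.05.

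- k = 49/42 = 1.167
- m = 49 × 0.04 + 42 × 0.19 = 1.96 + 7.98 = 9.94 events
- Power = Φ( √(k·m) × 0.75 / (k × 0.25 + 1) − 1.96 ) = Φ(3.405 × 0.75 / 1.292 − 1.96) = 50.7%, against 51% stated
- Ceiling with unlimited controls = Φ( √(49 × 0.19) × 0.75 − 1.96 ) = 62.9%, as stated

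These figures reproduce and do not depend on the censoring rule. What carries over is the event count: about 2 failures expected in SCOUT and 8 in the controls. If one of two SCOUT failures goes unrecorded, that arm's numerator is halved.

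**2. Effect of unascertained time, constant hazard.** Let a share f of an arm's person-time lie after failure status was last known, with no failures seen in it. The estimated hazard is then events / total time = true hazard × (1 − f). With shares f_E in SCOUT and f_C in the controls, the hazard ratio is multiplied by (1 − f_E)/(1 − f_C). All values of f below are assumptions, because the documents give none.

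| f_E | f_C | Multiplier |
|---|---|---|
| 0.10 | 0 | 0.90 |
| 0.20 | 0 | 0.80 |
| 0.30 | 0 | 0.70 |
| 0 | 0.20 | 1/0.80 = 1.25 |
| 0.20 | 0.20 | 1.00 |

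The direction therefore depends on which arm was followed less completely.

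**3. The same effect in a Cox model, SCOUT arm only.** This is a large-sample simulation with these assumptions:

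- exponential hazards, with 19% of controls failing by 24 months
- follow-up uniform on 12 to 48 months
- 20% or 43% of SCOUT patients having no failure seen from one month after the last dose
- median time to end of dosing of 12 or 24 months

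The 43% is 38/88, the Phase 1 share of all SCOUT tumours at July 2019 (protocol 7.5.1). The share among IFS patients is not given. The resulting unascertained share of SCOUT time is 7% to 22%.

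| True HR | Censored at last known alive date | Censored when status last known |
|---|---|---|
| 0.25 | 0.20–0.23 | 0.24–0.26 |
| 0.50 | 0.38–0.47 | 0.49–0.51 |
| 1.00 | 0.77–0.94 | 0.97–1.03 |

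**4. If failures come early.** With front-loaded hazards (Weibull shape 0.35 to 0.5, otherwise as in step 3), a true hazard ratio of 0.50 becomes about 0.43–0.44 at 22% unascertained time and 0.48 at 7%. The proportional rule would give 0.50 × 0.78 = 0.39 and 0.50 × 0.93 = 0.465. The bias shrinks but does not vanish.

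**5. Limits of steps 3 and 4.** They treat deaths in the unascertained period as unseen. In practice deaths would be seen, so these results lie towards the upper end for a given share.

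**The case against.** The strongest reply is that ascertainment may in fact be complete.

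- Protocol 9.3.1 expects start dates of later systemic therapy and radiotherapy, and dates of mutilating surgery, from the SCOUT case report forms, without separating the phases.
- Protocol 9.2.3.2 requires information on therapies and outcomes for a patient to be eligible.
- Protocol 9.2.3.1 excludes control sources with more than 10% missing outcome data.
- Protocol 9.8 describes source verification in SCOUT.
- SAP 3.1.2 keeps Phase 2 patients who stop the drug after a response or resection under evaluation.

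These points narrow the likely gap. None of them ties failure status to the last known alive date.

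A reader might infer from SAP 3.1.1 that Phase 1 had survival-only follow-up, and hence that the rule favours larotrectinib. The documents do not support that. SAP 3.1.1 does not say that later therapies went uncollected, and it refers to the SCOUT protocol for further Phase 1 detail. The control sources are also undescribed on this point. Protocol 9.9 warns that they may lack a pre-established protocol, and weaker ascertainment there would push the hazard ratio against larotrectinib.

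A fair point also stands about the remedy. If a source records events whenever they come to light but negative status only at visits, cutting event-free time at the last visit while keeping every event would overstate the hazard. The fix has to treat events and event-free time alike.

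**Conclusion.** The rule as written does not fit the endpoint, and this holds for both arms whatever SCOUT Phase 1 collected. Whether it does harm depends on how far failure status was known in each source, which the documents do not say. The direction is undetermined.

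The size is undetermined too. The factor (1 − f_E)/(1 − f_C) rests on constant hazards, on no failures (including deaths) being seen in the unascertained time, and on unknown shares. It is an illustration of scale, not an estimate. The simulated ranges look at the SCOUT arm alone and share the last two limits.

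The point is still worth acting on. With about 2 SCOUT failures expected, a single missed one would move the result, and no planned analysis would reveal it. The study is declared exploratory in the protocol abstract. That limits the consequences but does not make the rule suitable.

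**What to change.** Write one rule for both arms in SAP 6.2.1 and 6.3.1 to 6.3.4. Censor event-free patients at the last date on which systemic therapy, radiotherapy and surgery status was ascertained, for example the last clinical follow-up contact. Count events only up to each source's ascertainment cut-off, so that events and event-free time are treated alike. State how a death after a patient's last status date but before that cut-off is handled.

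Keep the last known alive date for OS, and as a sensitivity analysis for the primary endpoint. Report the gap between the two dates by arm, by control source and by SCOUT phase, and state what each source collected on later therapies.

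The cost is one derived date per patient and somewhat shorter follow-up. Where a source holds no dated negative status, the last clinical contact has to serve as a proxy, and the report should say so. If ascertainment was complete, the two dates will largely coincide and the result will barely change.
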